5.4.3.2 Over the whole trial

Similarly, duration of exposure, duration on actual dose, total dose and dose intensity will be summarized over the whole trial. Time to first dose reduction and time to first interruption will also be computed and shown.

Over this period, the categories for the duration of exposure will be: ≤ 3 months (91 days); > 3 months (91 days) to ≤ 6 months (182 days); > 6 months (182 days) to ≤ 12 months (365 days); > 12 months (365 days) to ≤ 18 months (547 days); > 18 months (547 days) to ≤ 24 months (730 days); > 24 months (730 days)

Time to first dose reduction, time to first treatment interruption, as well as time to premature treatment discontinuation will also be evaluated via survival methods. Censoring rules can be found in [Table 5.4.3.2: 1](#), [Table 5.4.3.2: 2](#) and [Table 5.4.3.2: 3](#) respectively.

Duration of exposure in patient years will also be shown per treatment group.

Table 5.4.3.2: 1 Censoring Rules for Time to first dose reduction over the whole trial

Rule #	Situation	Outcome (event or censored)	Date of event or censoring
1	Patient had a documented first dose reduction before the treatment was permanently discontinued or the patient switched into the extension trial and the date of the event is known	Event	Date of event
2	Patient had a documented first dose reduction before the treatment was permanently discontinued or the patient switched into the extension trial and the date of the event is unknown	Event	Imputed date of event
3	Patient did not have a documented first dose reduction before the treatment was permanently discontinued or the patient switched into the extension trial	Censored	Earliest date of permanent drug discontinuation, database lock or date of Informed Consent in extension trial ^[1]

^[1] Date of Informed Consent in extension trial is not applicable for the primary analysis.

Table 5.4.3.2: 2 Censoring Rules for Time to first treatment interruption over the whole trial

Rule #	Situation	Outcome (event or censored)	Date of event or censoring
1	Patient had a documented first treatment interruption before the treatment was permanently discontinued or the patient switched into the extension trial and the date of the event is known	Event	Date of event
2	Patient had a documented first treatment interruption before the treatment was permanently discontinued or the patient switched into the extension trial and the date of the event is unknown	Event	Imputed date of event
3	Patient did not have a documented first treatment interruption before the treatment was permanently discontinued or the patient switched into the extension trial	Censored	Earliest date of permanent drug discontinuation, database lock or date of Informed Consent in extension trial ^[1]

^[1] Date of Informed Consent in extension trial is not applicable for the primary analysis.

Table 5.4.3.2: 3 Censoring Rules for Time to premature treatment discontinuation over the whole trial

Rule #	Situation	Outcome (event or censored)	Date of event or censoring
1	Patient had a documented premature treatment discontinuation and the date of the event is known	Event	Date of event
2	Patient had a documented premature treatment discontinuation and the date of the event is unknown	Event	Imputed date of event
3	Patient did not have a documented premature treatment discontinuation and the patient switched into the extension trial	Censored	Earliest date of database lock or date of Informed Consent in extension trial ^[1]

[1] Date of Informed Consent in extension trial is not applicable for the primary analysis.

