⁴ In case of premature discontinuation of study medication, EOT_B should be done as soon as possible after last drug intake and a Follow-up Visit should be completed 4 weeks after EOT_B. A scheduled visit can be skipped if EOT_B or Follow-up Visit occurs within 4 weeks prior to scheduled visits. For patients who complete the study regularly, EOT_B should be scheduled after the Sponsor’s communication of the end of the trial. Only in case the patient does not roll-over in the separate open-label study a Follow-up Visit should be completed 4 weeks after EOT_B.

⁵ Urine dipstick pregnancy tests will be provided by central laboratory and should be performed in all women of childbearing potential at least at every visit and if necessary; additionally at home or at a local laboratory / local doctor every 4-6 weeks. If urine test is not acceptable to local authorities, a blood test can be done at a local laboratory. Documentation will be done in patient’s notes.

⁶ Resting ECG should be done at every other scheduled visit (i.e. Visit X)

⁷ Order of lung function measurements: 1. FVC followed by patients rest; 2. DLCO. Measurements at approximately the same time each visit, reference time at Visit 2.

⁸ Vital status at the time of the data cut-off for the primary analysis and at the end of the trial should be available for all randomized patients. Consent for a vital status call at respective time points in case of premature discontinuation of trial participation will be requested for all patients as part of the informed consent.

TABLE OF CONTENTS

CLINICAL TRIAL PROTOCOL	1
TITLE PAGE	1
CLINICAL TRIAL PROTOCOL SYNOPSIS	2
FLOW CHART PART A: 52 WEEKS TREATMENT PERIOD.....	6
FLOW CHART PART B¹: VARIABLE TREATMENT PERIOD BEYOND 52 WEEKS	9
TABLE OF CONTENTS	10
ABBREVIATIONS.....	14
1. INTRODUCTION.....	17
1.1 MEDICAL BACKGROUND.....	17
1.1.1 ILD Overview	17
1.1.2 PF-ILD disease concept	19
1.1.3 Patient population to be studied in the current trial	20
1.2 DRUG PROFILE	21
2. RATIONALE, OBJECTIVES, AND BENEFIT - RISK ASSESSMENT	26
2.1 RATIONALE FOR PERFORMING THE TRIAL	26
2.2 TRIAL OBJECTIVES.....	26
2.3 BENEFIT - RISK ASSESSMENT.....	26
3. DESCRIPTION OF DESIGN AND TRIAL POPULATION	29
3.1 OVERALL TRIAL DESIGN AND PLAN	29
3.1.1 Administrative structure of the trial	31
3.2 DISCUSSION OF TRIAL DESIGN, INCLUDING THE CHOICE OF CONTROL GROUP(S)	32
3.3 SELECTION OF TRIAL POPULATION	34
3.3.1 Main diagnosis for trial entry	34
3.3.2 Inclusion criteria	35

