[figure not shown]

Figure 3.1: 1

Study design schematic of study 1199.247 followed by a separate open label trial (optional): Part A (Visit 1 through 9 over 52 weeks) and Part B (Visit 10 through EOT Visit over variable period for each patient)

The primary assessment of benefit-risk of nintedanib in patients with PF-ILD will be based on efficacy and safety data over 52 weeks.

The primary analysis of this study will therefore be performed once the last randomized patient reaches the Week 52 Visit (Visit 9 at the end of Part A). At that time, a first database lock will occur and all the data will be unblinded. Efficacy and safety analyses will be performed on the data from Part A of the trial to assess the benefit-risk of nintedanib over 52 weeks. In addition, data collected in Part B of the trial (after 52 weeks) and available at the time of data cut-off for the primary analysis will be reported together with data from Part A (i.e. over the whole trial) (see [Section 5.1](#)).

After review of the efficacy and safety data available after the first data base lock, the Sponsor will communicate the end of the trial and an EOT_B visit has to be performed in all ongoing patients. Depending on the results of the evaluation, patients receiving trial medication until the end of Part B will be eligible for open-label treatment with nintedanib in a separate study.

Trial 1199.247 i.e. Part B will continue until all patients have completed the EOT_B visit and the Follow-up Visit as applicable. A final database lock will then occur and Part B data collected between the data cut off for the primary analysis and the final database lock will be reported together with data from Part A i.e. over the whole trial (see Section 5.1).

Concomitant treatment rules, dose reduction procedures and short term drug interruptions in case of adverse events are described in [Section 4.2](#).

For each patient, the study period is from the signature of the Informed Consent until their last visit. Adverse events are collected during the entire study period and are considered treatment-emergent from first study drug intake until 28 days after drug discontinuation.

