6.2.3 Follow-up Visit and trial completion

A Follow-up Visit has to be scheduled 28 days after End of Treatment Visit for all patients except for patients transferred into a separate open-label extension study. This Follow-up Visit is the safety follow-up after treatment discontinuation.

- Physical examination including vital signs.
- Adverse events and concomitant therapy will be assessment since last visit.
- Local dipstick pregnancy test (if applicable).
- FlowScreen® spirometry (FVC) in the allowed time window will be performed.
- Non-elective hospitalization will be recorded.
- Acute ILD exacerbations will be recorded.
- Patient's participation will be concluded for patients who withdraw consent and do not attend future visits.

Trial completion

The trial completion eCRF page has to be filled-in when the patient has terminated the trial. The end of the trial for the individual patient is:

- For patients who complete all study visits, end of trial is EOT_B. A follow-up visit is only required for those who do not roll-over in the separate open-label study
- For patients who withdraw consent
 - at time of trial medication discontinuation, end of trial is an EOT visit followed by a follow-up visit.

- after EOT was already completed, then the patient should have a final visit based on their scheduled study visit.

Patients who prematurely discontinued trial medication

In case a patient has to permanently discontinue trial medication, for whatever reason, he/she will be encouraged to attend all future visits up to end of trial as originally planned (except for the laboratory ‘a-Visits’).

- During these visits, the patient will undergo all planned examinations according to [Flowcharts A](#) and [B](#), especially FlowScreen® spirometry (FVC) and will fill in the PRO questionnaires (only Part A); however he/she will not have to do the resting ECG, safety laboratory, biomarker laboratory and PK blood draw.
- These visits will be regarded as part of the trial despite the patient having discontinued trial medication.

The need for coming to future visits in case of prematurely discontinuation of trial medication will be explained to patients prior to their participation in the trial.

Vital status information

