6.1.2 Over the whole trial

For efficacy and safety analyses over the whole trial period (Part A and Part B), data from first drug intake up to the last visit in the trial will be considered. Please see Table 6.1.2: 1 for details about analysis periods over the whole trial (Part A + Part B) according to the type of endpoint. For the main analysis only data collected over the whole trial available at the time of data cut-off for DBL1 will be considered, whereas all data collected within the trial will be considered and reported for the final analysis.

Table 6.1.2: 1 Summary of analysis periods over the whole trial (Part A and Part B) according to the type of endpoint or analysis

Type of analysis	Analyses / Endpoints	Studied period	
		Start date ^[2]	End date ^{[1][4]}
Efficacy analyses	Analyses on all endpoints listed in Sections 5.1.3.2 of the CTP	Date of first drug intake	Date of last measurement up to the last follow-up visit (included) or last contact date (as defined in Section 5)
Descriptive analyses over the trial period	Absolute change from baseline in: 
• FVC (ml)• FVC (% of predicted)• DLCO (% of predicted)• Vital signs Relative change from baseline in : 
• FVC (% of predicted)	Date of first drug intake	Date of last measurement up to last follow-up visit (included)
Efficacy survival analysis	Time to all-cause mortality (over the trial period)	Date of first drug intake	Last contact date (as defined in Section 5)
Extent of exposure analysis overall	See Section 5.4.3	Date of first drug intake	Date of last drug intake
Safety survival analysis ^[3]	Time to 
• first liver enzyme elevation (for all definitions mentioned in Section 5.4.4)• first onset of adverse event with additional information collection (diarrhoea, bleeding, ILD)	Date of first drug intake	Date of last drug intake + 28 days
	Time to 
• first dose reduction• first treatment interruption• premature treatment discontinuation	Date of first drug intake	Date of last drug intake
On-treatment safety analysis overall ^[3]	
• Adverse events• Laboratory data• Vital signs	Date of first drug intake	Date of last drug intake + 28 days

[1] End date is included.

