7.1 DEMOGRAPHIC AND OTHER BASELINE CHARACTERISTICS

A table in the CTR will present the number of patients screened, randomised and treated. The number of patients prematurely discontinuing their study treatment will be shown with the reasons for discontinuation. The number and percent of patients completing the end of treatment visit and the number of patients with treatment ongoing will also be presented. Please note there will be ongoing patients at the time of the data cut-off for the primary analysis; at the time point when the final analysis will take place there will not be any more ongoing patients in this trial. Where percentages are shown, the denominator will be the number of patients treated in each treatment group.

Descriptive statistics as well as frequency counts will be provided for all demographic and baseline characteristics depicted in [Section 5.4.1](#). The CTR tables will show the relevant descriptive statistics (number and percent within categories; other descriptive statistics for continuous variables) by treatment arm.

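### The whole-trial censoring rule for time to premature treatment discontinuation gives completers who do not roll over no date except the final database lock, after their last dose

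*SAP*

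**What the plan says.** SAP section 5.4.3.2 plans time to first dose reduction, time to first interruption and time to premature discontinuation over the whole trial by survival methods, each with its own censoring table.

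In Table 5.4.3.2: 3 (premature discontinuation), Rules 1 and 2 are events with a known or an imputed date. Rule 3 is the only censoring row. Its situation is "Patient did not have a documented premature treatment discontinuation and the patient switched into the extension trial", and its date is "Earliest date of database lock or date of Informed Consent in extension trial". The footnote to that date reads "Date of Informed Consent in extension trial is not applicable for the primary analysis".

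SAP Table 6.1.2: 1 sets the end of the studied period for the same endpoint, in the row shared with dose reduction and interruption, as "Date of last drug intake". Its footnote 4 limits the main analysis to data available at the cut-off for the first lock.

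Two groups of event-free patients who have not switched are foreseen:

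- **On drug at the first lock.** SAP section 7.1 states: "Please note there will be ongoing patients at the time of the data cut-off for the primary analysis". Under Protocol section 3.1 the extension depends on the review of the first-lock data, after which "patients receiving trial medication until the end of Part B will be eligible for open-label treatment with nintedanib in a separate study".
- **Completers who do not roll over.** Protocol section 6.2.3 provides for them: "A follow-up visit is only required for those who do not roll-over in the separate open-label study". Footnote 4 of the Part B flow chart adds: "Only in case the patient does not roll-over in the separate open-label study a Follow-up Visit should be completed 4 weeks after EOT_B".

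**The concern.** A censoring table should place every patient in exactly one row and stop the clock when the patient is no longer at risk. Rule 3 joins absence of the event to a switch into the extension with the word *and*, so its situation column describes only switchers. Its date column contains no end-of-treatment date.

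Part B exists to supply longer-term controlled data, and time on drug is a basic measure of tolerability. Two programmers, one working from Table 5.4.3.2: 3 and the other from Table 6.1.2: 1, could produce different curves at the final analysis. The first would hold completers who do not roll over at risk beyond the end of their treatment.

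**Working it through.** The plan states no figure to reproduce. The check maps each patient state to the text of the tables.

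| State without an event | Meets the Rule 3 situation as written? | Date the Rule 3 date column can give | End date in Table 6.1.2: 1 |
|---|---|---|---|
| Switched into the extension (final lock) | Yes | Earlier of lock and extension consent | Last drug intake |
| On drug at the first lock | No | First database lock (consent excluded by footnote) | Last drug intake, within data available at the first cut-off |
| Completed, no roll-over (final lock) | No | Final database lock (no consent date exists) | Last drug intake |

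**On drug at the first lock.** The footnote says how Rule 3 works at the primary analysis, when nobody can have switched. It makes sense only if the row is meant for patients who have not switched. With consent removed, database lock is the one date left. Footnote 1 of SAP Table 5.4.4: 2 (liver enzyme elevation) states the same convention openly for patients who have not yet stopped drug. The intent can be recovered; the situation text is wrong.

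**Completers who do not roll over.** Suppose Rule 3 is read generously to include them.

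1. They have no extension consent date, so the earliest of the two listed dates is the final lock.
2. Protocol section 3.1 places the final lock after all patients have completed EOT_B and, where applicable, the follow-up visit.
3. For these patients the follow-up visit is 4 weeks after EOT_B, that is 4 × 7 = 28 days.
4. If last intake is at about EOT_B, each of them therefore gains at least about 28 days of at-risk time after treatment has ended. The gain is longer for anyone whose EOT_B comes before that of the last patient.

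**Direction of the effect.** At a given time since first dose, let *d* patients discontinue prematurely, let *n* be truly on drug, and let *m* have completed but still be counted at risk. The Kaplan-Meier step uses *d*/(*n* + *m*) in place of *d*/*n*, so the hazard is multiplied by *n*/(*n* + *m*), which is below 1 whenever *m* is above 0. Cumulative discontinuation is understated wherever other patients discontinue at those durations. The documents give neither *m* nor the timing of those events, so no size follows.

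**Sister tables.** Tables 5.4.3.2: 1 and 2 (dose reduction, interruption) use *or* between permanent discontinuation and the switch, and they list permanent drug discontinuation among the censoring dates. Completers who do not roll over are therefore stopped correctly there. Table 5.4.3.2: 3 alone has *and* with no end-of-drug date. The 52-week counterpart, Table 5.4.3.1: 3, has no switch clause and censors every event-free patient at day 373.

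**The case against.** The strongest reply is that the documents already contain the right end point. Table 6.1.2: 1 ends the studied period at last drug intake, and a careful programmer would apply it. Whole-trial results are descriptive (Protocol section 7.3), no safety hypothesis is tested (Protocol section 7.3.4), the benefit-risk assessment rests on 52 weeks, and the explicit Kaplan-Meier plan for this endpoint is in the 52-week section (SAP 7.7.1). The number of completers who do not roll over is unknown.

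All of that stands, and it limits the weight of the point. It does not remove the conflict. Table 5.4.3.2: 3 is the endpoint-specific rule, it gives a different date, and nothing in the SAP says which table prevails.

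A reader might go further and infer that patients on drug at the first lock have no rule at all. On planned enrolment of 600, with an assumed 10% to 30% discontinuing, that would be 600 × 0.90 = 540 down to 600 × 0.70 = 420 patients, and a curve built only on patients with events would reach 100% discontinued. The documents do not support this. The date column and footnote show that these patients are to be censored at database lock, and SAP section 7.1 expects them. The discontinuation range is an assumption that comes from neither document.

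**Conclusion.** Rule 3 of Table 5.4.3.2: 3 is wrong as written and should be corrected. For patients still on drug at the first lock it is a wording error with a recoverable meaning. For completers who do not roll over it is a substantive error: the only date available falls after treatment has ended, which lowers the late part of the whole-trial discontinuation curve and contradicts Table 6.1.2: 1 and the two sister tables.

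The direction holds provided that some completers do not roll over and that other patients discontinue at the affected durations. The magnitude cannot be estimated from the documents. No efficacy result, confirmatory test or 52-week discontinuation curve changes.

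**What to change.** In Rule 3 of Table 5.4.3.2: 3, delete the clause requiring a switch into the extension trial, so that the row covers every patient without a documented premature discontinuation. Set the censoring date to the earliest of last drug intake in this trial (permanent drug discontinuation at the planned end of treatment), database lock, and extension consent, matching Tables 5.4.3.2: 1 and 2. State that patients still on drug at the first lock are censored at that lock, since their last intake has not yet occurred.

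If the data cut-off is preferred to the lock date, in line with footnote 4 of Table 6.1.2: 1, make that change in all the whole-trial exposure tables together. Otherwise the three exposure curves would stop the same patients at different dates.

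The core change is an edit to one row, with no new data and no effect on trial conduct. The optional move to data cut-off touches the sister tables as well.

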5.4.4 Liver enzyme and bilirubin elevations

Liver enzyme and bilirubin elevations will be reported using the three following definitions:

- (ALT and/or AST $\geq 3 \times \text{ULN}$) AND bilirubin $\geq 2 \times \text{ULN}^*$
- ALT $\geq 5 \times \text{ULN}$ and/or AST $\geq 5 \times \text{ULN}$
- ALT $\geq 3 \times \text{ULN}$ and/or AST $\geq 3 \times \text{ULN}$

*These elevations of ALT/AST/bilirubin are defined within a time window of 30 days i.e. the elevation of bilirubin should appear within 30 days after the elevation of AST and/or ALT.

Depending on the number of patients experiencing liver enzyme elevations, other cut-offs may be considered.

Signs of hepatic injury will also be presented based on the following definition:

- ALT and/or AST $\geq 8 \times \text{ULN}$
- ALT and/or AST $\geq 3 \times \text{ULN}$ and unexplained INR > 1.5 in the same sample
- ALT and/or AST $\geq 3 \times \text{ULN}$ and unexplained eosinophilia ($> 5\%$) in the same sample
- ALT and/or AST $\geq 3 \times \text{ULN}$ and presence of fatigue, nausea, vomiting, right upper abdominal quadrant pain or tenderness, fever and/or rash (see [Section 9.9](#) for details about MedDRA terms used to select relevant AEs) within $+/- 7$ days of the detected ALT or AST increase.

In addition, maximum individual elevations based on worst value on treatment will be defined as:

- $\geq 3 \times \text{ULN}$; $\geq 5 \times \text{ULN}$; $\geq 8 \times \text{ULN}$ for AST and ALT and AST and/or ALT
- $\geq 1.5 \times \text{ULN}$; $\geq 2 \times \text{ULN}$ for Bilirubin
- $\geq 1.5 \times \text{ULN}$; $\geq 2 \times \text{ULN}$ for alkaline phosphatase (ALK)

Time to first liver enzyme elevation will also be evaluated via survival methods. Censoring rules can be found in Table 5.4.4: 1 and [Table 5.4.4: 2](#) below.

Table 5.4.4: 1 Censoring Rules for Time to first liver enzyme elevation over 52 weeks

Rule #	Situation	Outcome (event or censored)	Date of event or censoring
1	Patient had a documented first liver enzyme elevation within the first 52 weeks or before the treatment was prematurely ^[1] discontinued and the end of the residual effect period (REP) has been reached, and the date of the event is known	Event	Date of event
2	Patient had a documented first liver enzyme elevation within the first 52 weeks or before the treatment was prematurely ^[1] discontinued and the end of the REP has been reached, and the date of the event is unknown	Event	Imputed date of event
3	Patient did not have a documented first liver enzyme elevation within the first 52 weeks or before the treatment was prematurely ^[1] discontinued and the end of the REP has been reached.	Censored	If day of last drug intake < 372 days after first drug intake: Date of last drug intake +28 days or date of death (if earlier) ^[2] If day of last drug intake \geq 373: Date of first drug intake + 372 days

[1] Prematurely: Discontinuation of the treatment before completion of Visit 9.

[2] Patients that die between date of permanent drug discontinuation and the end of the residual effect period will be censored at their date of death

Table 5.4.4: 2 Censoring Rules for Time to first liver enzyme elevation over the whole trial

Rule #	Situation	Outcome (event or censored)	Date of event or censoring
1	Patient had a documented first liver enzyme elevation before the treatment was permanently discontinued and the date of the event is known	Event	Date of event
2	Patient had a documented first liver enzyme elevation before the treatment was permanently discontinued and the date of the event is unknown	Event	Imputed date of event
3	Patient did not have a documented first liver enzyme elevation before the treatment was permanently discontinued	Censored	Earliest date of database lock, date of permanent drug discontinuation + 28 days or date of death ^{[1][2][3]}

^[1] Date of permanent drug discontinuation may not have been reached when the primary analysis takes place. In this case, the date of database lock will be used.

^[2] Patients who switch to the extension study will only be evaluated until date of last drug intake in this study. The residual effect period will not apply, as patients will receive continuous treatment

^[3] Patients that die between date of permanent drug discontinuation and the end of the residual effect period will be censored at their date of death.

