7.8.1.4 Adverse events with additional information collection

Diarrhoea, bleeding and ILD are AEs with additional AE-specific information collected on the eCRF. These are investigator reported on the eCRF and will be identified using this information for this analysis. That is if the diarrhoea information has been completed for an adverse event then the adverse event will be considered as diarrhoea for this analysis regardless of subsequent MedDRA coding of the verbatim term. Likewise, if the bleeding information has been completed for an adverse event then the adverse event will be considered as bleeding for this analysis regardless of subsequent MedDRA coding of the verbatim term. The same applies to ILD.

The frequency of patients with AEs with additional information collection will be summarised by treatment, primary SOC and PT separately for diarrhoea, bleeding and ILD. The additional information collected will also be summarised at the AE level rather than at the patient level separately for diarrhoea, bleeding and ILD. For the time to first onset of diarrhoea, bleeding or ILD, respectively, Kaplan-Meier plots by treatment will be created. The same censoring rules as for time to first liver enzyme elevation will be used. See [Table 5.4.4: 1](#) and [Table 5.4.4: 2](#) for details. Please note that these evaluations are prepared for the co-primary populations, as well as in the complementary population, and covering both analysis periods “over 52 weeks” and “over the whole trial”.

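### SAP Table 5.4.4: 2 stops counting first liver enzyme elevations at permanent discontinuation but follows patients for 28 more days, contradicting the SAP's own analysis window

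*SAP*

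**What the plan says.** SAP Section 5.4.4, Table 5.4.4: 2, sets the whole-trial rules.

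- **Rule 1 (event):** "Patient had a documented first liver enzyme elevation before the treatment was permanently discontinued and the date of the event is known". Rule 2 is the same with an imputed date.
- **Rule 3 (censored):** "Patient did not have a documented first liver enzyme elevation before the treatment was permanently discontinued". The censoring date is "Earliest date of database lock, date of permanent drug discontinuation + 28 days or date of death".
- **Footnotes:** footnote 1 substitutes database lock for patients still on treatment at the primary analysis. Footnote 2 removes the residual effect period (REP) for rollover patients: "Patients who switch to the extension study will only be evaluated until date of last drug intake in this study". Footnote 3 censors at death any patient who dies between discontinuation and the end of the REP.

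Three other places bear on the same analysis.

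- **Table 5.4.4: 1 (52 weeks)** has an REP clause in its event rules: "discontinued and the end of the residual effect period (REP) has been reached, and the date of the event is known".
- **Table 6.1.2: 1** ends the whole-trial safety survival period for liver enzyme elevation, diarrhoea, bleeding and ILD at "Date of last drug intake + 28 days", end date included.
- **Section 7.8.1.4** says of the diarrhoea, bleeding and ILD curves: "The same censoring rules as for time to first liver enzyme elevation will be used". It points to both tables.

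**The concern.** In a time-to-event analysis, the period in which an event can be counted and the period in which a patient is treated as at risk should be the same. In Table 5.4.4: 2 they differ by up to 28 days. A patient whose first elevation is found in the REP fails Rules 1 and 2, meets the condition of Rule 3, and is carried as event-free beyond the date of the elevation.

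The 52-week and whole-trial displays could then contradict each other on the same patient, with the longer analysis holding fewer events than the shorter one for the same stretch of follow-up. A programmer working from the SAP also has two incompatible instructions for one display: Table 5.4.4: 2 and Table 6.1.2: 1.

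**Working it through.** The documents state no event count, power or other figure for this endpoint, so there is nothing to reproduce. The check applies the two sets of rules to the same patients.

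**1. Test patient.** Last intake on day 400, database lock on day 700, no extension study, alive. Take the discontinuation date as the date of last intake. The follow-up end is min(700, 400 + 28) = day 428.

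| First elevation on day | Table 5.4.4: 2, literal | Table 6.1.2: 1 window |
|---|---|---|
| 390 | event, day 390 | event, day 390 |
| 401 | censored, day 428 | event, day 401 |
| 410 | censored, day 428 | event, day 410 |
| 428 | censored, day 428 | event, day 428 |
| 429 | censored, day 428 | censored, day 428 |

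The rules disagree on every day from +1 to +28. Day 400 itself depends on how strictly Rule 1's condition on timing is read.

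**2. The same patient in the two periods.** Suppose last intake is on day L in Part A, with L + 28 before day 373, and the first elevation is on day L + 10. Under the 52-week table, with its REP clause, this is an event on day L + 10. Under the whole-trial table it is censored at day L + 28.

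**3. Which reading the SAP intends.** Footnotes 2 and 3 make sense only if the REP is time at risk. Treatment-emergent adverse events (Section 7.8.1) and the exposure-adjusted time at risk (Section 7.8.1.5) also run to 28 days. The whole-trial tables for dose reduction and interruption (Tables 5.4.3.2: 1 and 5.4.3.2: 2) use a similar pre-discontinuation condition but add no 28 days to the censoring date, so they are coherent. Table 5.4.4: 2 appears to have had its censoring date extended but not its event rules.

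**4. Scale, by assumption.** Protocol Section 1.2 gives adverse-event discontinuation in the IPF trials as 19% on nintedanib and 13% on placebo. Suppose those shares of 300 per arm stop without rolling over, and at least 28 days before lock:

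- nintedanib: 0.19 × 300 = 57 patients; 57 × 28 = 1,596 days; 1,596 / 365.25 = 4.4 patient-years
- placebo: 0.13 × 300 = 39 patients; 39 × 28 = 1,092 days; 1,092 / 365.25 = 3.0 patient-years

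This is follow-up in which no event can be counted. It is not a count of lost events.

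For events, the same section gives 5.0% of nintedanib patients with AST or ALT at least 3 × ULN: 0.050 × 300 = 15. The number first seen in the REP is unknown. Over an assumed range of 0 to 5, the crude proportion counted is:

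- 0 lost: 15/300 = 5.0%
- 1 lost: 14/300 = 4.7%
- 3 lost: 12/300 = 4.0%
- 5 lost: 10/300 = 3.3%

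**The case against.** The strongest reply is that this is a drafting slip that the rest of the SAP already resolves. Table 6.1.2: 1 and footnotes 2 and 3 show the intended window, and a careful programmer would follow them. That stands as to intent. It does not remove the conflict, because Table 5.4.4: 2 is the operative rule and Section 7.8.1.4 sends the reader to it.

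A reader might go further and infer that the last scheduled liver test is lost by design, and that hepatic and bleeding risk on nintedanib is therefore understated. The documents do not support this.

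- **Timing of the end-of-treatment laboratory.** The Part B flow chart says "EOT_B should be done as soon as possible after last drug intake". The Part A footnote on EOT_A has no such wording. The SAP does not equate the discontinuation date with last intake, and the flow chart records medication termination at EOT_B. Whether the laboratory sample falls after the discontinuation date is not settled.
- **Events that cause withdrawal.** These are generally documented before it, and so count even under the literal rule. Higher adverse-event discontinuation on nintedanib does not by itself mean more lost events there.
- **Tests in the window.** The Part B follow-up visit has no safety laboratory. The window is not empty, though. Protocol Section 4.2.1.2 has liver values re-tested for about two weeks after some permanent discontinuations. SAP Section 5.4.4 lets the bilirubin part of the combined definition follow the transaminase rise by up to 30 days. Adverse events are collected at follow-up.
- **Other outputs.** The treatment-emergent adverse event tables, the incidence rates and the on-treatment laboratory summaries already run to 28 days after last intake.

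**Conclusion.** The inconsistency is real and rests on the text alone: Rules 1 to 3 of Table 5.4.4: 2 give a wrong result for any first event in the REP, and Section 7.8.1.4 spreads this to three more curves.

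Its reach is narrow. It affects descriptive whole-trial Kaplan-Meier displays. The liver plot is produced only if at least 5% of patients have elevations (Section 7.8.2.1, applied to the whole trial by 7.8.2.2); no such threshold is stated for the diarrhoea, bleeding and ILD curves. Rollover patients, and those still on treatment at lock, do not have the 28-day gap. The primary endpoint, its multiplicity control and the power are untouched.

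The number of REP events and the direction of any between-arm bias cannot be determined from the documents. The patient-year and percentage figures above are illustrations that borrow IPF rates and, for the lost events, an assumed range. They are not estimates for this trial.

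**What to change.** In Table 5.4.4: 2:

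- In Rules 1 to 3, replace the condition tied to permanent discontinuation with one that runs up to and including the end of the residual effect period, 28 days after last drug intake.
- In the censoring column and footnotes, use last drug intake as the reference date, as Tables 5.4.4: 1 and 6.1.2: 1 do. Keep database lock and death as earlier limits.
- Keep the footnote 2 exception, so that rollover patients are followed only to last intake.

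State in Section 7.8.1.4 that the corrected rule applies to the diarrhoea, bleeding and ILD curves.

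The cost is one SAP wording change and one programming condition. No new data are needed.
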